A Clinical Trial of Silver Diamine Fluoride to Arrest Early Childhood Caries in Young Children

NCT04054635

Study Protocol and Statistical Analysis Plan

15 April 2019

Purpose:

To investigate the effectiveness of using silver diamine fluoride (SDF) to arrest early childhood caries in very young children randomized to different application frequency regimens. We will also study potential oral microbiome changes in children receiving SDF treatment.

Hypotheses:

1. Two applications of SDF at different frequencies will yield similar arrest rates.
2. SDF will negatively influence the population of cariogenic bacteria in the oral microbiome.

Objectives (*primary objective, †secondary objectives):

1. Determine the effectiveness of various application regimens of SDF to arrest caries*;
2. Determine potential changes to the oral microbiome in young children†; and
3. Determine the impact on early childhood oral health related quality of life†.

Methods:

Design: We propose a RCT to study the use of SDF to arrest cavitated caries lesions in primary teeth at different application regimens. Regimen 1 will be two applications of SDF four months apart, which is the protocol frequency adopted by the Winnipeg Regional Health Authority's Clinical Guideline on SDF. This frequency was used in a pilot study. Regimen 2 will be two applications of SDF six months apart (American Dental Association's [ADA] recommendation). Regimen 3 will be two applications of SDF one month apart, which is proposed in the American Academy of Pediatric Dentistry's clinical practice guideline. The ADA recently indicated that SDF should be prioritized over 5% NaFV for nonrestorative management of cavitated lesions. Thus, we will not include a control group to receive fluoride varnish as this would now be considered unethical and substandard care. However, we will attempt to follow as a comparison group those children whose parents/caregivers do not consent to SDF to manage their child's caries and only choose 5% NaFV.

Arrest of caries lesions will be determined by assessing clinical hardness, colour change, and size of lesions at baseline, at second visit, and at the final study visit. Children will be recruited and we will perform block randomization by site in order to achieve equal proportions in each regimen by clinic site of recruitment. Study visits will occur at the Children's Hospital Research Institute of Manitoba (CHRIM) or at community-based dental clinics. Following informed consent the child's parent/caregiver will complete a short questionnaire (via interview) on general and dental health, oral hygiene, dietary intake of sugars, and family demographics along with the ECOHIS to assess OHRQL. SDF will be applied on the day of recruitment to cavitated lesions involving dentin followed by 5% NaFV. Depending on which frequency regimen children are randomized to, they will return for a second visit. During this second visit, caries lesions treated with SDF at baseline will be assessed to see if caries is arrested as determined through measures of hardness, colour change, and size. At this same visit a second application of SDF will be applied to these initially treated caries lesions followed by 5% NaFV. Children and parents will return for the third and final study visit according to the schedule of their randomized grouping. Parents/caregivers will complete a follow-up questionnaire similar to the

baseline tool. Caries lesions previously treated by SDF will be assessed for clinical hardness, colour change and size to determine if they have arrested.

Population: As ECC is age specific, participants will be < 72 months of age with active caries and their parents/caregivers. The majority will be recruited from community-based dental clinics in Winnipeg (i.e., Access Downtown, Mount Carmel Clinic, and SMILE Plus Children's Dental Clinic) or who are currently on a wait list for dental surgery under general anesthesia in Winnipeg. We found that these were ideal sites for our recently completed feasibility trial of SDF. We will restrict participation to children living in the Winnipeg region or within a one hour drive of Winnipeg to minimize the risk of loss-to-follow-up. Eligibility criteria are designed to select young children who have active caries, and thus are at an increased risk of morbidity from existing caries and onset of new caries.

Inclusion Criteria: 1) Child is < 72 months of age with ECC with active caries lesions; 2) Child has ≥ 1 primary tooth with caries that is eligible to receive SDF. Eligible primary teeth must: a) have soft cavitated caries lesions extending into dentin (ICDAS 5 or 6); b) the cavitated lesions must allow for direct application of SDF. Teeth that meet any of the PUFA criteria (i.e. spontaneous pain due to caries, pulp exposure, mobility, signs of pulpal infection such as abscess, fistula, or swelling) will be excluded. However, a child would still be eligible even if they have at least one tooth that meets PUFA criteria, but other eligible teeth with caries do not.

Exclusion Criteria: 1) Child is allergic or has sensitivity to silver or other heavy metal ions; 2) Child has hereditary generalized developmental defects of enamel (e.g., amelogenesis imperfecta, dentinogenesis imperfecta); 3) Child has severe medical problems that limit participation; 4) Child requires immediate rehabilitation under general anesthesia because of severe infection or pain; 5) Antibiotic use within the last 2 weeks (for the microbiome sub-study).

Sample and Justification of Sample Size: Sample size for this pilot study has been determined in discussion with [name] (collaborator, Professor & Biostatistician). Our intent is to compare arrest rates between groups and to see whether the three different regimens will yield arrest rates within a range of what we will determine to be clinically acceptable. Based on our recent pilot feasibility study of SDF with 40 children (with 239 lesions) we reported an arrest rate of approximately 96% following two applications of SDF. Results from a recent systematic review state that 80% of lesions can arrest because of SDF. We believe that a range of arrest rates from 80% to 96% yield similar beneficial outcomes in the clinical setting. Based on our pilot study, 40 children had 239 lesions (average 6 lesions/child). With our pilot sample of 239 lesions, it is possible to estimate an arrest rate with a 95% confidence interval to be accurate within $\pm 6.5\%$. With 400 lesions anticipated in our proposed recruitment sample, the 95% confidence interval for the arrest rate would be $\pm 5.0\%$. We propose three SDF regimen groups and anticipate that each group will have 22 children anticipating an average of six lesions. This would mean 396 lesions would be followed in this study. We anticipate that with 400 lesions the percent of arrest will be within $\pm 5\%$ if we have 22 children in each group. To deal with potential drop-outs and loss-to-follow-up of up to 20% we will over recruit by into each group and recruit 28 per group. We anticipate that we can successfully recruit 10 children each month.

Instrumentation and Outcome Measures: Baseline and follow-up visit questionnaires will be a modified versions of those used in our SDF pilot feasibility study (developed by [name] [collaborator] in her SDF efficacy study). The questionnaire collects child and family

demographic information, oral hygiene and use of toothpaste, dietary habits (i.e., snack foods and drinks), consumption of fluoridated water, appearance of the teeth, and symptoms (e.g., pain). The tools also include sections for the parent/caregiver to complete with their child on how the child believes their teeth look and feel and how they rated their visit and SDF treatment.

The Early Childhood Oral Health Impact Scale (ECOHIS) will be used to assess changes in OHRQL from baseline to completion of study. ECOHIS is a validated tool for use with parents/caregivers of children < 72 months of age. It consists of 13 questions grouped into two sections: 1) child impact, and 2) family impact. The child impact section includes nine questions in four areas: 1) symptoms, 2) functions, 3) psychology, and 4) self-image and social interaction. The family impact component covers two areas: 1) parental distress and 2) family function. Each question is scored from 0 to 5 [0= never, 1= hardly ever, 2= occasionally, 3 = often, 4= very often, 5= don't know]. A total score for each child is calculated by summing up response codes. The ECOHIS will allow us to calculate and compare mean ECOHIS scores at each visit and between groups. Our team has experience with analyzing ECOHIS.

Clinical outcomes assessed will include the proportion of teeth arrested (i.e., "arrest rate" = total number teeth arrested / total number of teeth treated), the proportion of children with any arrested caries, associated morbidity (dental pain and, dental abscess assessed using the PUFA index), and proportion of children requiring dental surgery under GA. The PUFA index is a score of the consequences of severely decayed teeth with visible pulpal involvement (P/p), ulceration caused by dislocated tooth fragments (U/u), fistula (F/f) and abscess (A/a). We will also record dmft and dmfs scores for each child at baseline and at subsequent study visits. The dmft and dmfs scores are cumulative counts of the total number of primary teeth or surfaces decayed, missing due to, or filled because of caries.

Caries activity will be determined according to hardness and colour of the caries lesion. Hardness is the best indicator of dentinal tissue caries activity. We will assess the hardness of caries lesions by applying light force to the caries lesion with a ball ended probe and will classify the lesion into one of three hardness categories: 1) very soft; 2) medium; or 3) very hard. Hardness is associated with arrested caries. We will record these ratings of hardness of lesions on the Clinical Record Forms at the baseline visit, second visit, and third (final) clinical visit. The Clinical Record Forms will be those used in our pilot feasibility study of SDF. The colour of caries lesions will also be assessed. Dentin colour of each caries lesion will be classified as: 1) yellow; 2) brown; or 3) black. The colour black is associated with arrested caries. The size of caries lesions will also be measured (in mm) at the baseline, second, and third clinical visits.

Problems and adverse events will be recorded reported to the University of Manitoba's ethics office.

Implementation: Research staff will regularly visit community-based dental clinics in the Winnipeg region to recruit participants. Clinical dental staff at these sites will also be briefed on the study, its objectives, and eligibility criteria so that they can inform parents/caregivers of the study and make referrals to the research team. We will also recruit participants who are on the Children's Hospital dental clinic's wait list for pediatric dental surgery. Recruitment posters will also be placed in patient waiting areas of the various dental clinics and the study advertisements will also be distributed to all dentists in the Winnipeg region via the Manitoba Dental Association's weekly email distribution list. From our past study experiences we know that we can recruit at least 10 participants each month.

Our research staff will contact interested parents/caregivers and will inform them of the study objectives, eligibility criteria, and procedures. Children will undergo a dental screening by the principle investigator or a calibrated and trained dental examiner to determine whether children meet the clinical criteria for this study by having cavitated caries lesions involving dentin (i.e. ICDAS category 5 or 6). Since ECC is more common in disadvantaged populations, we will arrange for transportation (i.e., taxis) for participants. We also anticipate that some participants will be newcomers and will require interpreters. We will arrange for WRHA interpreters when needed. Visits will occur at the principle investigator's dental suite at CHRIM or at one of the community-based clinics.

Baseline visit: Following written informed consent, children will be randomly allocated into one of three groups using sealed envelopes to ensure random allocation. Parents/caregivers will complete the baseline questionnaire administered by interviewer. Children will undergo a dental examination (without x-rays) to record the number of teeth and tooth surfaces with caries meeting ICDAS 5 or 6 criteria and the specific tooth numbers. We will record the location, size, hardness, colour, and activity status of each eligible caries lesion. We will also assess the total number of primary teeth and tooth surfaces affected by caries (i.e., dmft and dmfs). We will also determine the PUFA index. SDF will then be applied with a microbrush for one minute to each cavitated lesion meeting the eligibility criteria followed by 5% NaFV.

Second visit: Depending on the regimen children will return 4 months (Regimen 1), 6 months (Regimen 2), or 1 month (Regimen 3) later for their first follow-up visit and second application of SDF. Parents/caregivers will complete the ECOHIS tool. Prior to the second application of SDF, caries lesions that received the first application of SDF will be assessed to determine if caries is arresting. Lesions will be assessed for colour change, size, and hardness. Clinical data will be recorded including dmft, dmfs, and PUFA scores will be recorded. Following the dental assessment of the lesions under investigation, SDF will be applied to these lesions for one minute followed by 5% NaFV.

Third visit: Depending on the regimen children will return 4 months (Regimen 1), 6 months (Regimen 2), or 1 month (Regimen 3) later for their final follow-up visit. Parents/caregivers will complete a follow-up questionnaire administered by interviewer. Caries lesions that were treated with applications of SDF will be assessed to see if caries is arrested. Caries lesions will be assessed for colour change, size, and clinical hardness. We will also record dmft, dmfs, and PUFA scores. Clinical data will be recorded on the Clinical Record Form.

Clinical data from baseline and each follow-up visit will be linked with questionnaire data. Data will be entered into a REDCap database and saved on the secure server at CHRIM.

Oral Microbiome Sub-Study: SDF may inactivate cariogenic bacteria in vitro. There was only one study that conducted RNA analysis of plaque in six children before and after treatment (3 receiving SDF and 3 placebo) reporting no changes in relative abundance of cariogenic bacteria. In that study, not only was sample size a major limitation, but the lead author is a director of Advantage Arrest™. Our proposal to assess 30 children would provide statistical power and help elucidate if SDF leads to changes in the oral bacteriome and mycobiome. This will provide novel insights into SDF's mechanism of action, whether antimicrobial, remineralization, or both. Ten children from each regimen will have plaque samples collected. Samples will be obtained at baseline (prior to SDF application), at the first follow-up visit (prior to SDF application), and at the final visit. Nucleic acid isolation from plaque samples will be done using the DNeasy

PowerSoil Kit (Qiagen). It allows the isolation of genomic DNA (gDNA) from fungi and Gram (+-) bacteria, which will be used for downstream analyses. For the 16S rRNA (bacteriome) and ITS1 rRNA (mycobiome) amplicon sequencing, isolated gDNA will be used for PCR amplification of the V4 region of the bacterial 16S rRNA gene, and for PCR amplification of the fungal Internal Transcribe Spacer 1 (ITS1) rRNA gene. gDNA will be sequenced at Génome Québec using paired-end Illumina MiSeq PE250 sequencing. Data analysis will be performed in the [name] lab using established methods. Briefly, demultiplexed raw sequencing results will be filtered and clustered into operational taxonomic units (OTUs) and alpha and beta diversity analyses performed using QIIME2 (Quantitative Insights into Microbial Ecology) v. 2018.11. 16S sequences will be aligned and taxonomy assigned with the HOMD database. ITS1 sequences will be aligned and taxonomy assigned with the UNITE database.

Data Analysis:

This study will estimate the success of different SDF. Descriptive statistics will be used (e.g. frequencies, proportions, and means \pm standard Deviations). The “arrest rate” (primary outcome) will be calculated for the second visit and again at the third and final visit. Bivariate analyses will assess changes in clinical measures and survey data from baseline to the follow-up. McNemar’s test will be used to compare the arrest rate between the second and third clinical visits and to compare dichotomous data from the baseline questionnaire with that from the follow-up questionnaire within each regimen. Chi-squared analysis will compare arrest rates between the regimen groups. Paired t-test will be used to compare normally distributed interval data from the baseline questionnaire with that from the follow-up questionnaire within regimens (Mann-Whitney test if not normally distributed). We will rely on repeated measures analysis of variance to assess changes in ECOHIS scores and other continuous data over time (i.e. baseline vs. second visit vs. final study visit) within each regimen group and to assess differences between regimen groups. Although this is a pilot RCT, we will explore potential changes in the oral microbiome of those randomized to different regimens. This will provide insights into potential mechanisms of SDF action, whether it has antimicrobial activity and influences the oral microbiome composition. A p value ≤ 0.05 will be significant.

Ethics:

An application will be submitted to the University of Manitoba’s Biomedical Research Ethics Board by the June 2019. Additional approvals are being sought from the WHRA and Mount Carmel Clinic. Considering some participants will be First Nations, we will notify Nanaandawewigamig before starting this RCT, although First Nations status will not be a covariate in our data analysis. Written informed consent will be obtained from parents or legal guardians of the child. The consent form will state that parents/caregivers are free to withdraw at any time, without any effect on the child’s dental treatment at the dental clinic they attend. Patients of the PI are eligible to participate. However, he will not obtain consent from parents/caregivers of his own patients. At the end of this RCT we will offer SDF to parents to manage any new caries lesions that have developed on their child’s other teeth or surfaces or those lesions not eligible in this RCT (i.e., ICDAS 3 and 4).

Knowledge Translation (KT):

Study outcomes will be disseminated at conferences and in publications. [name] is a Canadian Institute for Health Research Embedded Clinician Researcher and is integrated into

the Winnipeg Regional Health Authority and Shared Health, providing opportunity to share findings with stakeholders responsible for oral health policy and programs. We will also work with our knowledge users (Drs. [name], [name], and [name]). We will rely on established networks to share our findings. [name] co-leads (and [name] is a member of) the Healthy Smile Happy Child initiative, which promotes early childhood oral health in Manitoba. Telehealth and Zoom conferencing are used for these activities. Drs. [name] and [name] are part of Nanaadawewigamig's Canadian Institutes for Health Research Partners for Engagement and Knowledge Exchange, which will disseminate evidence to communities. [name] also leads the Oral Health and the Aboriginal Child Knowledge Transfer website where findings will be disseminated (> 35,500 page views). The Canadian Dental Association's Knowledge Networks will assist with knowledge translation to inform dental professionals, stakeholders, researchers, and the public. [name] is strategically positioned as chair of the Canadian Dental Association's Committee on Clinical and Scientific Affairs, which provides another avenue to disseminate findings to inform policy and clinical guidelines on SDF.

Significance and Future Directions:

SDF may be a simple and non-invasive agent to arrest caries in children. Before SDF can be implemented in dental public health programs and Indigenous communities it is important to study which application regimen is most effective and appropriate. CHRIM funding will provide essential information on the ability for SDF to arrest ECC and will inform a future CIHR application to conduct a scaled-up RCT of SDF with high-risk children, including those from Indigenous, newcomer, rural, and disadvantaged communities.

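### Hypothesis 1 predicts similar arrest rates, but the only planned between-regimen test is a chi-squared test that cannot show similarity and ignores clustering of teeth or lesions within child

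*Combined protocol and SAP*

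**What the plan says.** Under Hypotheses, the first hypothesis is that "Two applications of SDF at different frequencies will yield similar arrest rates". Under Sample and Justification of Sample Size, the purpose is put this way: "Our intent is to compare arrest rates between groups and to see whether the three different regimens will yield arrest rates within a range of". The sentence goes on to make clinical acceptability the basis for that range. The same section adds: "We believe that a range of arrest rates from 80% to 96% yield similar beneficial outcomes in the clinical setting".

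The size is justified by precision, not power. "With 400 lesions anticipated in our proposed recruitment sample, the 95% confidence interval for the arrest rate would be" ±5.0%, and the pilot's 239 lesions are said to give ±6.5%. The 400 comes from three regimens of 22 children with about six lesions each: "This would mean 396 lesions would be followed in this study".

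Under Instrumentation and Outcome Measures, the arrest rate is defined by teeth: "total number teeth arrested / total number of teeth treated". Under Implementation (baseline visit), it is children who are randomised.

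Data Analysis opens with "This study will estimate the success of different SDF" and lists descriptive proportions. For arrest rates it names two tests: McNemar's between the second and third visits, and chi-squared between regimens. The significance level is p ≤ 0.05. It gives no margin on a difference, no interval for a difference, and no allowance for several teeth or lesions per child. Repeated-measures analysis of variance is reserved for ECOHIS and other continuous data.

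**The concern.** The null hypothesis of a chi-squared test is equality. Failing to reject it may mean that the regimens are alike or that the trial is too small to tell, so it cannot carry Hypothesis 1. The 80% to 96% range is the nearest thing to a similarity criterion. It describes absolute rates, is not a margin on a difference, and does not appear in the analysis.

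The test is also invalid as a test of difference if outcomes within a child are correlated. It counts teeth or lesions, while the independent unit is the child. Positive correlation raises its false-positive rate. McNemar's test on the same teeth or lesions has the same defect.

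Finally, the precision offered for the sample size belongs to one overall rate. Comparing regimens needs the precision of each regimen and of each difference, and neither is given. The sample-size section also counts lesions where the outcome definition counts teeth.

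At stake are the error rates for the primary outcome, in a study whose Significance section says it will inform an application for a larger trial.

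**Working it through.** **Inputs from the documents.** 3 regimens; 22 evaluable children per regimen; about 6 lesions per child, so 22 × 6 = 132 lesions per regimen and 3 × 132 = 396 in all; arrest rates of 80% (systematic review) and 96% (pilot).

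**Assumptions.** ICC of 0, 0.1 or 0.3; 3 or 4 treated teeth per child for the tooth-level figures. The documents give neither.

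**1. The plan's own precision.** At p = 0.5 and z = 2 the half-width is 1/√n. For n = 239 this is 6.47%, and for n = 400 it is 5.00%. Both stated figures reproduce, as one proportion over all lesions taken as independent. With z = 1.96 they are 6.34% and 4.90%.

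**2. Precision for the comparison.** Half-width = 1.96 × √(p(1−p) × DE / 132), with DE = 1 + (6 − 1) × ICC = 1, 1.5, 2.5. For a difference between two regimens, multiply by √2. Example: p = 0.80, ICC 0: 1.96 × √(0.16/132) = 6.8%, and × √2 = 9.7 points.

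| Quantity | ICC 0 | ICC 0.1 | ICC 0.3 |
|---|---|---|---|
| One regimen, 80% | ±6.8% | ±8.4% | ±10.8% |
| One regimen, 96% | ±3.3% | ±4.1% | ±5.3% |
| Pairwise difference, 80% | ±9.7 points | ±11.8 | ±15.3 |
| Pairwise difference, 96% | ±4.7 points | ±5.8 | ±7.5 |

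**3. False positives of the planned chi-squared test.** As an approximation, the unadjusted three-group statistic behaves as DE times a chi-squared variable on 2 degrees of freedom, so the error rate is P(χ²₂ > 5.99/DE) = exp(−2.996/DE). This is 0.05, 0.136 and 0.302 at ICC 0, 0.1 and 0.3. Beta-binomial simulation, with equal true rates of 80%, 90% or 96%, agrees:

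| Units per child | ICC 0 | ICC 0.1 | ICC 0.3 |
|---|---|---|---|
| 6 lesions | 5% | 13-14% | 29-31% |
| 3-4 teeth (assumed) | about 5% | 7-10% | 13-21% |

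**4. Missed differences, same test, 6 lesions per child.**

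| True rates | ICC 0 | ICC 0.1 | ICC 0.3 |
|---|---|---|---|
| 85/85/76% | 52% | 48% | 42% |
| 96/96/87% | about 18% | 20% | 22% |

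Both rows have one regimen 9 points lower. Near the pilot rate the test is much less likely to miss it. A drop across the plan's whole range, 96/96/80%, is missed less than 4% of the time. In the first row the miss rate falls as the ICC rises because the uncorrected test rejects too readily, which is not real sensitivity.

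**The case against.** The study calls itself a pilot and says that it will estimate success, so a demand for power or a formal equivalence test would be out of place. That stands, and it favours estimates with valid intervals over the planned test. It does not rescue the test, because the plan still sets a significance threshold for it. The Significance section also asks which regimen is most effective. Chi-squared does address a difference, but only validly with clustering allowed for.

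Four stronger readings are tempting and should not be drawn.

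- A reader might infer that the ±5% is a mistake or is claimed for each regimen. It reproduces, it uses the conservative p = 0.5, and the text ties it to all 400 lesions. What is missing is the precision for a regimen or a difference. At 96% a single regimen is within ±5% at ICC 0 and 0.1.
- A reader might infer that the sponsor will treat a non-significant result as proof of Hypothesis 1. Nothing says so. The plan simply names no other between-regimen analysis of arrest rate by which to judge it.
- A reader might infer that a 9-point shortfall is missed about half the time in general. That holds at 85/85/76%, rates which the documents do not give; at 96/96/87% it is 18% to 22%.
- A reader might take the 29-31% false-positive rate as established. It needs an ICC of 0.3 and six lesions per child. On the outcome as defined, by teeth, it is smaller.

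**Conclusion.** The point holds. The planned between-regimen analysis cannot support Hypothesis 1, makes no use of the 80% to 96% range, and has the wrong error rates whenever outcomes within a child are positively correlated. That conclusion needs no particular ICC. Its size does: false positives run from the nominal 5% with no correlation to about 13-14% (ICC 0.1) or 29-31% (ICC 0.3) by lesions, and 7-10% or 13-21% by teeth at an assumed three to four per child. The pooled ±5% is correct but does not serve the comparison. This should be fixed before analysis; it does not call for a change in design or recruitment.

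**What to change.** 1. **Data Analysis, estimation.** Base Hypothesis 1 on each regimen's arrest rate after two applications and on the pairwise differences, all with 95% confidence intervals that allow for clustering within child. Show the per-regimen intervals against the plan's own 80% to 96% range. Any standard cluster method will do (GEE or a mixed logistic model, for example) provided a fallback is named for a regimen with no failures, such as design-effect-adjusted Wilson and Newcombe intervals. At 96% arrest, at least one regimen has no failures in about 1%, 4% and 15% of simulated trials (ICC 0, 0.1, 0.3). State that the pairwise intervals are not adjusted for multiplicity.
2. **Data Analysis, tests.** Replace the unadjusted chi-squared and McNemar tests of arrest rate with cluster-adjusted versions. State that a non-significant result is not evidence of similarity, and that a formal similarity claim needs a difference margin which the sponsor prespecifies and justifies.
3. **Sample and Justification of Sample Size.** Keep ±5%, labelled as pooled over regimens and assuming independent lesions. Add per-regimen and pairwise precision at 80% and 96%, with a design effect over a range of ICCs informed by the pilot. A range is needed because 40 children at 96% arrest estimate the ICC poorly: in simulation, a true 0.1 gives estimates from −0.02 to 0.26 (5th to 95th percentile).
4. **Unit.** Use either tooth or lesion in the sample-size, outcome and analysis sections. If tooth, define when a tooth with several lesions counts as arrested.

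**Cost.** No more children: revised wording, an ICC from data the sponsor already holds, and some programming. The stated precision becomes less favourable, the similarity conclusion may be inconclusive, and the adjusted tests reject less often. At 85/85/76%, the adjusted chi-squared is significant 45%, 35% and 22% of the time (ICC 0, 0.1, 0.3), against 48%, 52% and 58% unadjusted, where part of the apparent gain is false-positive inflation.

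### Randomisation is blocked by recruitment site, but no between-regimen analysis uses site; a correct child-level analysis without it would be conservative if site predicts arrest

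*Combined protocol and SAP*

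**What the plan says.** Under Methods, Design, allocation is tied to site: "we will perform block randomization by site in order to achieve equal proportions in each regimen by clinic site of recruitment". The Population paragraph names three community clinics ("Access Downtown, Mount Carmel Clinic, and SMILE Plus Children's Dental Clinic") and adds children on a wait list for dental surgery under general anaesthesia. The Baseline visit paragraph says "children will be randomly allocated into one of three groups using sealed envelopes to ensure random allocation", without saying whether the envelopes are prepared by site.

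The Data Analysis section gives two between-regimen methods. For the primary outcome: "Chi-squared analysis will compare arrest rates between the regimen groups". For quality of life: "We will rely on repeated measures analysis of variance to assess changes in ECOHIS scores and other continuous data over time", within and between regimen groups. Neither has a site term or stratum. The threshold is "A p value ≤ 0.05 will be significant". The only statement about covariates is in the Ethics section: "First Nations status will not be a covariate in our data analysis". The sample-size section uses neither site nor a design effect.

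**The concern.** Blocking by site takes between-site variation out of the contrast between regimens, because each regimen gets nearly the same mix of sites. An analysis without site still counts that variation as error. The estimated standard error is then larger than the true one, and the test rejects less often than its nominal level.

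That would be a cautious error in many trials. Here the first hypothesis is that the regimens give similar arrest rates, while the planned test looks for a difference. Overstated standard errors make a non-significant result easier to obtain, and it could be read as support for similarity. With 22 evaluable children per group there is little precision to give away. A site effect is plausible because the wait list and the community clinics may recruit different children, but the documents do not establish one.

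**Working it through.** **The plan's own figures.** With lesions treated as independent and p = 0.5, the half-width is 1.96 × √(0.25/n). For n = 400 this is 4.90% (stated as 5.0%); for n = 239 it is 6.34% (stated as 6.5%). Total lesions: 3 × 22 × 6 = 396. Recruitment: 22/0.80 = 27.5, rounded up to 28 per group. These agree to rounding, and none involves site.

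**Inputs for the site check.** From the documents: three regimens, blocking by site, 66 evaluable children (3 × 22), about six lesions per child, α = 0.05. Assumed: four equal recruitment strata (three clinics plus the wait list), a two-sided test, and a share s of between-child variance in arrest explained by site.

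**Child-level F test without site.** Set total between-child variance to 1, with N children and error df = N − 3.
- True variance relevant to the regimen contrast: 1 − s.
- Expected error mean square without site: (1 − s) + s × N/(N − 3).
- Ratio r = the first divided by the second. The standard error is overstated by the factor 1/√r.
- Approximate true type I error: P(F(2, N − 3) > F crit / r).

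For N = 66, F crit = 3.143:

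| s | Error mean square | r | SE factor | F crit / r | Type I error |
|---|---|---|---|---|---|
| 0 | 1.000 | 1.000 | 1.000 | 3.143 | 5.0% |
| 0.10 | 0.9 + 0.1 × 66/63 = 1.0048 | 0.896 | 1.057 | 3.509 | 3.6% |
| 0.20 | 0.8 + 0.2 × 66/63 = 1.0095 | 0.792 | 1.123 | 3.966 | 2.4% |

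With N = 72 (a fully balanced layout of 4 sites × 3 regimens × 6 children) or N = 84 (all recruited), the factors stay at about 1.056 and 1.122 to 1.123, and the error rates at 3.6% and 2.4%.

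**What the shares mean as arrest rates.** The site share of child-level variance is V/(V + W(1 + 5ρ)/6). Here V is the variance of the site rates, W the mean of p(1 − p), ρ the within-child correlation and 6 the lesions per child.
- Site rates 82/86/90/94%: V = 0.0020, W = 0.1036. Share 10% at ρ = 0, 5.5% at 0.2, 3.7% at 0.4.
- Site rates 75/85/93/97%: V = 0.0071, W = 0.1023. Share 29% at ρ = 0, 17% at 0.2, 12% at 0.4.

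So with correlated lesions, a 20% share needs site differences slightly wider than the second set.

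**Simulation with binary lesions.** 72 children, six lesions each, beta-binomial within child, 10,000 runs per scenario. For power, one regimen was lower by 0.9 on the logit scale. Ranges and sequences run over ρ = 0, 0.2, 0.4.

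| Site rates | Type I error without site | with site | Power without site | with site |
|---|---|---|---|---|
| Equal (88%) | 0.047–0.051 | 0.046–0.050 | 0.86, 0.56, 0.41 | 0.86, 0.56, 0.41 |
| 82/86/90/94% | 0.037–0.041 | 0.045–0.052 | 0.79, 0.50, 0.36 | 0.84, 0.54, 0.39 |
| 75/85/93/97% | 0.015–0.028 | 0.044–0.050 | 0.63, 0.40, 0.29 | 0.82, 0.52, 0.37 |

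**The chi-squared as written.** In the same runs, the test on lesions had type I error of 0.214 and 0.207 (moderate and large site differences) at ρ = 0.2, and 0.374 and 0.353 at ρ = 0.4. Stratifying by site left it at 0.220 and 0.230, and at 0.384 and 0.380. At ρ = 0, stratifying moved power only from 0.846 to 0.853 and from 0.812 to 0.837.

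**ECOHIS.** If site adds a constant c to a child's score at every visit, the change is (Y₂ + c) − (Y₁ + c) = Y₂ − Y₁, so site drops out. Comparisons of level between regimens keep c in the error term.

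**The case against.** The strongest objection is that the conservative direction does not describe the primary test as planned. The arrest rate is defined on teeth, with about six lesions per child, and the planned chi-squared treats them as independent. A reader might infer from the missing site term that the primary p-values will be too large. The documents do not support that: unless within-child correlation is negligible, the net error runs the other way, and site stratification does not correct it. This stands, and the point is limited accordingly.

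The size is also uncertain. The documents give no site-specific rates. The plan's own view is "We believe that a range of arrest rates from 80% to 96% yield similar beneficial outcomes in the clinical setting", which concerns regimens and says nothing about sites. Eligibility narrows severity: only ICDAS 5 or 6 lesions qualify, and teeth meeting PUFA criteria and children needing immediate treatment under general anaesthesia are excluded. A 20% share is therefore at the large end. The number of strata is not fixed either, since only the majority of children come from the listed sources and advertisements go to all dentists in the region. This stands as a limit on size.

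Omitting a balanced factor creates neither bias nor false positives, and the study is a pilot. That is true, but the remedy is nearly free, and a conservative difference test is not neutral when similarity is the hypothesis.

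Finally, the statement about First Nations status might be read as ruling out covariates generally. It concerns that one variable; on site the plan is silent.

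**Conclusion.** The mismatch between design and analysis is real: site governs allocation and appears in no between-regimen analysis. For a child-level analysis, omitting site overstates the standard error by about 6% to 12% and lowers type I error to about 3.6% to 2.4% if site explains 10% to 20% of between-child variance. In the simulation, the power lost was about 2 to 5 points with moderate site differences and 8 to 19 with large ones. With no site effect there is no loss. These figures assume four equal strata, balanced regimens within site, and site differences that the documents do not give.

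The point covers between-regimen comparisons only. The within-regimen McNemar and paired tests are unaffected, and little change is expected in the regimen-by-time comparison of ECOHIS. It is a worthwhile refinement and secondary to accounting for clustering within child.

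**What to change.** - **Arrest.** Include site of recruitment in a between-regimen analysis that also accounts for clustering within child. Options are GEE or mixed logistic regression with regimen and site as factors, or a site-stratified analysis of child-level arrest proportions. A site-stratified test on individual teeth is not enough.
- **ECOHIS.** Include site in the between-regimen comparison of levels.
- **Small sites.** Define site as the stratum used for randomisation, say where children recruited outside the listed sources belong, and set a rule before analysis for pooling very small sites.
- **Consistency.** State in the Baseline visit paragraph whether the sealed envelopes are prepared by site, in line with the Design section.

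The cost is one extra term per model. Site must already be known in order to randomise by it, so no new data are needed. The downside is possible sparse cells in small sites if arrest is near 96%, which the pooling rule is meant to limit.
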